11.2.2 Statistical methods

Demographics and baseline characteristics of patients will be summarized using descriptive statistics.

The analyses of the all endpoints will occur at 12 months after the last evaluable patient is recruited.

No imputation for missing data is intended.

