17. Study Follow-Up Visits - follow-up assessments (e.g visits @ 1, 3, 6, 9, 12, 15, 18, 21 and 24 months post end of SABR Treatment) should be undertaken within \pm 14 days of the scheduled time point. In the event of overlapping visits (i.e. between day 1 of each pembrolizumab cycle and post-SABR follow-up visits), only one visit is required but all protocol mandated investigations (for both timepoints) must be undertaken.

18. All patients will be followed for survival until the last evaluable patient completes 12 months of follow-up. Participants who start a new systemic therapy, are retreated with pembrolizumab or who have distant progression will be followed for survival only.

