9.1.2 Treatment Schedule

Radiation therapy should commence within 4 weeks of patient registration on the study. A single dose of 20 Gy should be prescribed, although a single 18Gy fraction can be used as an alternative for a centrally located lung lesion or a spinal lesion with a SINS score of ≥ 7 after review at SABR chart round. Typically a single fraction of 20Gy should be prescribed for spinal vertebral lesions, however, for those with a SINS score of ≥ 7 after review at SABR chart round, a single 18Gy fraction is preferred.

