10.5 Survival Follow-up

All patients will be followed for survival until the last evaluable patient completes 12 months of follow-up.

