11.2.4 Time-to-event analysis

A cut-off date for follow-up will be determined at the time of analysis. The cut-off date will be chosen to enable data on follow-up to that date to be collected, where possible, on all living patients. All events occurring after this date will be ignored in the analysis in order to minimise reporting bias.

The Kaplan-Meier method will be used to describe TTLP, DPFS and OS curves. Estimates at 1 and 2 years will be provided with 95% confidence interval. TTLP will be assessed at lesion level and Kaplan-Meier estimates will be adjusted for patient effect.

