11.2.9 Sample Size Calculation

This is a Phase Ib/II study to evaluate the safety profile and efficacy that would then be evaluated in a larger and more appropriately powered future study. The sample size of 30 patients is pragmatic.

The primary objective of the study is to provide a description of the safety profile of the combined SABR and pembrolizumab therapies. Table 8 illustrates different scenarios for grade 3 or 4 AEs rate ranging from 0% to 40% with the respective 95% exact confidence intervals, assuming 30 patients.

Table 8: Confidence Intervals for Adverse Event Rates

Number of patients with grade 3+ AE	Grade 3+ AE rate	95% confidence interval
1	3%	0% - 17%
2	7%	1% - 22%
3	10%	2% - 27%
4	13%	4% - 31%
5	17%	6% - 35%
6	20%	8% - 39%
7	23%	10% - 42%
8	27%	12% - 46%
9	30%	15% - 49%
10	33%	17% - 53%
11	37%	20% - 56%
12	40%	23% - 59%

Expected toxicities related to the pembrolizumab treatment are listed in the Investigator's Brochure. Therefore, immune related events such as hypothyroidism, pneumonitis, and colitis are expected. They should occur in <5%. Pneumonitis and colitis are considered to be the most serious but are rare events. Immune events and other events of clinical interest will be monitored for closely in this study, with early stopping rules as detailed below.

Recruitment will occur over a two-year period. An interim analysis after 15 patients completes 6 months of follow-up will be conducted for presentation purpose. The final analyses will be at the completion of 12 months after the last participant has completed SABR treatment.

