13.5 Data Management

Trial participants are to be identified by initials and trial registration number. All de-identified study data collected on electronic CRFs and source documents will be kept in a separate study specific de-identified database at BaCT. All trial data required for the monitoring and analysis of the study will be recorded electronically on the Electronic Data Capture e-system provided by BaCT. All required data entry fields must be completed. Data corrections will be done according to the instructions provided. Site investigators will be asked to confirm the accuracy of completed eCRFs by signing key eCRFs as indicated.

Source documents pertaining to the trial must be maintained by investigational sites and copies provided to BaCT when requested. Source documents may include a subject's medical records, hospital charts, clinic charts, the investigator's subject study files, as well as the results of diagnostic tests such as laboratory tests, and electrocardiograms. The investigator's copy of the case report forms serves as part of the investigator's record of a subject's study-related data. BaCT will conduct analysis from data stored in the patient database, kept in a secure location, with all de-identified. BaCT shall complete two reports: the first report will be after 15 patients completes 6 months of follow-up for presentation purpose only and the final report will be at 12 months from the completion of the last participant's SABR treatment.

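### Section 11.2.2 times the final analysis from the last recruitment, 11.2.9 and 13.5 from the last SABR; the two dates can differ by up to about 1 to 2 months

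*Combined protocol and SAP*

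**What the plan says.** Three sections date the same final analysis.

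- Section 11.2.2 (Statistical methods): "The analyses of the all endpoints will occur at 12 months after the last evaluable patient is recruited".
- Section 11.2.9 (Sample Size Calculation): "The final analyses will be at the completion of 12 months after the last participant has completed SABR treatment".
- Section 13.5 (Data Management): "the final report will be at 12 months from the completion of the last participant's SABR treatment".

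These cannot be separate planned analyses. Section 13.5 foresees only two reports: an early one for presentation once 15 patients have 6 months of follow-up, and the final one.

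Other text bears on which date is meant. Section 10.5 says: "All patients will be followed for survival until the last evaluable patient completes 12 months of follow-up". Sections 10.1.14 and 10.4 and footnote 12 of the Schedule of Events close imaging follow-up in the same way. Footnote 17 counts the visits from SABR: "visits @ 1, 3, 6, 9, 12, 15, 18, 21 and 24 months post end of SABR Treatment", each within 14 days either side. Section 7.14 starts OS, TTLP and DPFS at the commencement of SABR. The Trial Summary gives 24 months of enrolment and an estimated duration of 36 months.

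On the data cut-off, section 11.2.4 says: "A cut-off date for follow-up will be determined at the time of analysis". It adds that the date should allow follow-up to be collected on all living patients where possible, and that later events are ignored.

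**The concern.** Recruitment and the end of SABR are not the same day. Section 9.1.2 says: "Radiation therapy should commence within 4 weeks of patient registration on the study". Sections 9.1 and 9.1.13 then allow up to 21 calendar days to treat all lesions. Under 11.2.2, the analysis therefore falls before the last patient's nominal 12-month visit.

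This matters most for summaries tied to a visit. Section 11.2.1 makes a patient response-evaluable only if a scan was done at the visit concerned, 11.2.6 reports ORR at 12 months, and 11.2.2 rules out imputation. A patient whose 12-month scan falls after the cut leaves the 12-month denominator for an administrative reason. The 12-month pain score and the 12-month blood sample, for which 11.2.7 plans a baseline to 12-month contrast, are exposed in the same way.

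The wording also differs on whose date counts: the last evaluable patient in 11.2.2, the last participant in 11.2.9 and 13.5. Under 8.2, someone who has SABR but no pembrolizumab is not evaluable, so these can be two different people. In an open-label, single-arm trial, it is better not to leave a choice between two written dates until the data are in hand.

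**Working it through.** **The plan's own figure.** 24 months enrolment + 12 months = 36 months. The Trial Summary's duration is reproduced and allows nothing for the time between registration and SABR, so it agrees with 11.2.2.

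**Inputs.** 30 evaluable patients (8.2) over 24 months (8.1): 30/24 = 1.25 per month, or one every 0.8 months if accrual is even (an assumption). Radiotherapy starts 0 to 4 weeks after registration (9.1.2). SABR spans 0 to 21 days, ideally one day (9.1.13). If conventional radiotherapy is needed, footnote 3 of the Schedule of Events has it finished before SABR. Its longest course is 12 fractions (9.1.3), which is 12/5 = 2.4 weeks if five are given per week (an assumption). The documents give only maxima for the lags, no expected values.

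**Formula.** Let L be the time from registration to the end of SABR, in months (weeks × 7/30.44). At the 11.2.2 date, a patient is short of 12 months if recruited less than L before the last patient. With even accrual, the count is the number of i = 0, 1, 2, ... with 0.8 × i < L. With random uniform accrual, the expected count is about 1 + 1.25 × L, which simulation confirmed. The 1 is the last patient, who is short at any positive lag.

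| Lag, same for every patient | L (months) | Even accrual | 1 + 1.25L |
|---|---|---|---|
| 1 week | 0.23 | 1 | 1.3 |
| 2 weeks | 0.46 | 1 | 1.6 |
| 4 weeks | 0.92 | 2 | 2.2 |
| 7 weeks (4 weeks + 21 days) | 1.61 | 3 | 3.0 |
| 9.4 weeks (4 + 2.4 + 3) | 2.16 | 3 | 3.7 |
| 9.4 weeks, visit also 14 days late | 2.62 | 4 | 4.3 |

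The 3 at 7 weeks is borderline (2 × 0.8 = 1.60 < 1.61).

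**Varying lags (simulation).** If lags are uniform on 0 to 4 weeks with single-day SABR, the mean is 1.6 patients, and exactly one patient is short in 56% of runs. If uniform on 0 to 7 weeks, the mean is 2.0, with exactly one in 36%. With a lag of 2 weeks or less, the 12-month visit can be made up to 14 days early and so by the cut, and possibly nobody misses it.

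**Last patient's follow-up from the end of SABR at the 11.2.2 date.** 12 − 0.92 = 11.1 months at 4 weeks, 12 − 1.61 = 10.4 at 7 weeks, 12 − 2.16 = 9.8 at 9.4 weeks.

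**Time-to-event endpoints.** The clock starts at SABR commencement, so the 21-day span does not count. Without conventional radiotherapy, the shortfall is at most 4 weeks (0.92 months).

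**Acute safety.** Cycle 8 falls 7 × 21 = 147 days after cycle 1, which is at most 5 + 3 = 8 days after the last SABR. Adding 30 days gives 147 + 8 + 30 = 185 days. With a 49-day lag, that is 234 days from registration, well inside 12 months for a patient dosed on schedule.

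**Duration under the SABR anchor.** 24 + L + 12 = 36.9 months at 4 weeks, 37.6 at 7 weeks, 38.2 at 9.4 weeks.

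**The case against.** The strongest reply is that 11.2.2 is a stray sentence. Two other sections name the SABR date, and follow-up stays open until the last evaluable patient has 12 months. That stands as evidence of intent, and it means data collection itself would not stop at recruitment plus 12 months. It does not settle the matter, because the 36-month duration fits the other reading and 11.2.2 is the section that fixes the analysis date for every endpoint.

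A second reply is that 11.2.4 has a criterion for the cut-off. It does, and this softens the effect. But a cut-off chosen at the time of analysis does not say which anchor applies.

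A reader might go further and infer that the 12-month data of 2 to 4 patients would be lost. The documents do not support this:

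- The lags are permitted maxima, and same-day treatment of all lesions is preferred.
- Four patients need conventional radiotherapy first, the longest SABR span and a late visit together, or clustered accrual.
- Patients censored a few weeks before one year still contribute to the Kaplan-Meier estimates.
- Progression awaiting its 4 to 6 week confirmation is a feature of any cut, including the SABR-based one.
- Late toxicity is collected to 24 months after SABR (10.8.2), so it is incomplete for later patients under either date.

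**Conclusion.** The contradiction is real: one final analysis has two dates. Section 11.2.2 gives the earlier one and is out of line with the visit schedule and the closure of follow-up. Followed literally, it would leave the last patient, and about 1 to 3 of 30 in all, up to about 1 to 2 months short of 12 months from SABR. This rests on even accrual of 1.25 per month and on lags for which the plan gives only upper limits. The plausible range runs from possibly no missed visit to 4 patients in an extreme case.

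The practical effect is small. It falls on the 12-month ORR, pain score and blood sample, which have no imputation. The Kaplan-Meier endpoints are censored slightly early, the acute part of the primary safety endpoint is largely unaffected, and the analysis is descriptive (11.1). It should still be corrected, because the analysis date should be fixed once and in advance, and the correction is nearly free.

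**What to change.** 1. Replace the sentence in 11.2.2 so that 11.2.2, 11.2.9 and 13.5 all use one anchor: 12 months after the last evaluable patient completes SABR. This also removes the difference between last evaluable patient and last participant.
2. In 11.2.4, tie the cut-off to that date in advance, and state whether a 12-month assessment made within its +14-day window is included. Simply adding 14 days, or a wait for confirmatory scans, would create a third date and clash with 11.2.9, 13.5 and the rule to ignore later events, unless those were amended too.
3. Align the 36-month estimated duration in the Trial Summary, which becomes up to about 37 to 38 months at the permitted lags.

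The cost is wording, plus a final report up to about 1 to 2 months later than under the recruitment-based reading.

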11.2.3 Safety analysis

Safety will be assessed using CTCAE v4.03 and the maximum toxicity grade of each adverse event will be derived and presented in table format. The proportion of patients who suffer from grade 3 or higher toxicities (each toxicity and overall) will be provided along with its exact 95% CI for all patients who have received at least one dose of pembrolizumab and completed at least one SABR treatment. Events of clinical interest will be also tabulated (see Section 10.8.5.3 Events of Clinical Interest).

11.2.4 Time-to-event analysis

A cut-off date for follow-up will be determined at the time of analysis. The cut-off date will be chosen to enable data on follow-up to that date to be collected, where possible, on all living patients. All events occurring after this date will be ignored in the analysis in order to minimise reporting bias.

The Kaplan-Meier method will be used to describe TTLP, DPFS and OS curves. Estimates at 1 and 2 years will be provided with 95% confidence interval. TTLP will be assessed at lesion level and Kaplan-Meier estimates will be adjusted for patient effect.

11.2.5 Pain analysis

Pain will be described as change over time using linear mixed models. The linear mixed model will include time (as a factor) as fixed effect and patients as random effect. Mean and 95% confidence intervals will be calculated for each time point and the data will be displayed graphically. If strong floor effect is observed or if the assumptions of the model do not hold, simple descriptive statistics will be provided instead for each time point.

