6.3 Secondary Objectives

Secondary objectives are to examine evidence of clinical efficacy of the combination:

1. To describe overall survival (OS).
2. To describe time to local progression (TTLP).
3. To describe distant progression free survival (DPFS).
4. To describe overall response rate (ORR).
5. To describe disease control rate (DCR)
6. To describe changes in pain ratings over time.

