7.10 Summary of Risks and Benefits

SABR involves highly hypofractionated radiotherapy given as an ablative treatment. While there is extensive literature suggesting that it is safe and has low rates of major toxicities, such studies have tended to have small numbers and relatively short follow up given most patients succumb to their metastatic disease. Thus, by combining a short course of immunotherapy after SABR, we postulate that this will result in a lower likelihood of patients succumbing to further disease recurrence.

The risk of SABR treatment depends on the exact anatomical site of the oligometastatic disease irradiated. There is a low but not negligible risk of radiation pneumonitis, bone fractures, radiation enteritis, skin fibrosis, renal impairment and proctitis. There is an exceedingly low risk of transverse myelitis.

SABR is thought to provide long-term local control of known oligometastatic sites of cancer. It also provides good and durable pain relief for painful metastases. It is postulated that SABR to sites of oligometastatic or oligoprogressive renal cell carcinoma, in selected patients, may prolong survival. Clearly studies that determine whether a survival benefit occurs with such treatment remain to be conducted and reported.

It is acknowledged that patients may have received previous radiotherapy to an area where SABR is to be delivered in this protocol (equivalent dose of 30 Gy in 10 fractions). Due to the increased dose that is received in this instance, there is an increased risk of radiation toxicity in these patients. This potential increased level of risk has been highlighted in the patient information and consent form and must be discussed in each instance prior to informed consent. Patients who have received more than this RT equivalent dose schedule to an area planned for further SABR treatment are not eligible for this study.

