8.3 Participant Inclusion Criteria

In order to be eligible for participation in this trial, the participant must:

1. Has provided written informed consent for the trial.
2. Be ≥ 18 years of age on day of signing informed consent.
3. Have oligometastases (1-5 metastases), and measurable disease based on RECIST 1.1.
4. Participants must have a histologically or cytologically confirmed metastatic renal cell carcinoma. Oligometastatic lesions do not need to be biopsied but they must be clinically consistent to represent metastatic disease.

5. Patient can either be treatment naïve or have previously received up to 2 lines of systemic treatment (eg. Pazopanib or Sunitinib). If patient has received prior systemic therapy, the total number of metastases that have not been treated with definitive local therapies should not number more than 5.
6. Must have had surgical consideration for metastasectomy and thought appropriate for SABR due to medical inoperability, technical factors or patient declining surgery.
7. Must have at least one metastasis for which SABR is technically deliverable.
8. Be willing to provide archival tissue from a previously biopsied or excised primary or metastatic RCC lesion (if available). If safe to do so, a request for newly obtained specimen (obtained up to 5 weeks prior to trial registration) will be made, however participation for this biopsy is entirely optional.
9. Have a performance status of 0-2 on the ECOG Performance Scale (Appendix 1)
10. Demonstrate adequate organ function as defined in Table 3, all screening labs should be performed within 10 days of registration.

Table 3: Adequate Organ Function Laboratory Values

System	Laboratory Value
Haematological	
Absolute neutrophil count (ANC)	$\geq 1.5 \times 10^9/L$
Platelets	$\geq 100 \times 10^9/L$
Haemoglobin	$\geq 90 \text{ g/L}$ or $\geq 5.6 \text{ mmol/L}$ without transfusion or EPO dependency (within 7 days of assessment)
Renal	
Serum creatinine OR Measured or calculated ^a creatinine clearance (GFR can also be used in place of creatinine or CrCl)	$\leq 1.5 \times$ upper limit of normal (ULN) OR $\geq 30 \text{ mL/min}$ for participant with creatinine levels $> 1.5 \times$ institutional ULN
Hepatic	
Serum total bilirubin	$\leq 1.5 \times$ ULN OR Direct bilirubin \leq ULN for participants with total bilirubin levels $> 1.5 \times$ ULN
AST (SGOT) and ALT (SGPT)	$\leq 2.5 \times$ ULN OR $\leq 5 \times$ ULN for participants with liver metastases

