11.2 Statistical Analysis Plan

11.2.1 Populations for Analyses

- Enrolled participant population includes all participants who provided informed consent.
- Treated participant population (evaluative patients) is defined as the participants who completed at least one SABR treatment and received at least one dose of pembrolizumab. This is the primary population for the safety and efficacy analyses.

- Response-evaluable participants are those treated participants who have CT/MRI scans performed at respective follow-up visit.

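### The floor-effect fallback for pain (Section 11.2.5) names no within-patient change, so differences between visits can mix change in pain with change in who is still attending

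*Combined protocol and SAP*

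**What the plan says.** Secondary objective 6 in Section 6.3 is: "To describe changes in pain ratings over time". Section 11.2.5 sets the model: "The linear mixed model will include time (as a factor) as fixed effect and patients as random effect". Its output is: "Mean and 95% confidence intervals will be calculated for each time point and the data will be displayed graphically". No contrast with baseline is named for pain, although Section 11.2.7 names baseline contrasts for the exploratory markers. The fallback reads: "If strong floor effect is observed or if the assumptions of the model do not hold, simple descriptive statistics will be provided instead", again for each time point. No threshold is given for a strong floor effect.

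Four other places bear on this:

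- **Population.** Section 11.2.1 says of the treated patients: "This is the primary population for the safety and efficacy analyses". The disease criterion in Section 8.3 is: "Have oligometastases (1-5 metastases), and measurable disease based on RECIST 1.1". No criterion there asks for pain.
- **Follow-up.** Footnote 18 to the Schedule of Events, repeated in substance in Section 10.4, says: "Participants who start a new systemic therapy, are retreated with pembrolizumab or who have distant progression will be followed for survival only". Section 11.2.2 plans no imputation.
- **Timing.** Section 7.14 collects pain before conventional radiotherapy (CRT) where it is given, before SABR, before each pembrolizumab cycle, and then every 3 months to 24 months. Section 11.2.5 does not say which score is baseline.
- **Expected benefit.** Section 7.10 says of SABR: "It also provides good and durable pain relief for painful metastases".

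**The concern.** Because pain is not an entry requirement, some patients will probably score zero at the start, and a floor effect is a realistic prospect. If it appears, the plan leaves the one analysis that links a patient's visits and moves to summaries visit by visit, without asking for change within patients.

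The patients seen at month 12 need not be those seen before SABR, since several disease-related events end pain follow-up. A fall or rise between two visit summaries could then come from patients leaving. At stake is how a reader interprets the pain results of a single-arm trial, where no control group would reveal such a shift.

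A second, smaller matter is that nothing in the plan describes pain separately in patients who have it at entry, which is where Section 7.10 expects relief.

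**Working it through.** **1. The plan's own figure.** There is none to reproduce. The documents give no effect size, SD, power, baseline prevalence or drop-out rate for pain. Only n = 30 comes from the plan (Section 11.2.9). All other inputs below are assumptions.

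**2. Visit means when nobody changes.** Assume 10 of 30 patients have pain with mean 4.5, 20 score 0, and no patient's score changes. Drop-out is unrelated to the score among those with pain.

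Visit mean = (patients with pain still attending × 4.5) / (all still attending). At baseline it is (10 × 4.5)/30 = 1.5.

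| Left by month 12: with pain / pain-free | Still attending | Visit mean | Apparent change | Paired change |
|---|---|---|---|---|
| 60% / 30% | 4 + 14 = 18 | (4 × 4.5)/18 = 1.0 | -0.5 | 0 |
| 40% / 40% | 6 + 12 = 18 | (6 × 4.5)/18 = 1.5 | 0 | 0 |
| 30% / 60% | 7 + 8 = 15 | (7 × 4.5)/15 = 2.1 | +0.6 | 0 |

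The one-third fall in the first row exists only because more patients with pain were assumed to leave. Equal drop-out removes it, and the opposite pattern reverses it. Paired change is zero throughout.

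**3. Visit means when patients with pain improve.** A simulation used 300 trials of 30 patients. Assumptions: baseline pain about 5 (SD 1.5) in those with pain, a fall of about 2 (SD 1.5, scores bounded at 0 and 10), no change in pain-free patients, and drop-out of 50% with pain and 20% without.

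| Share with pain | True all-patient change | Difference of visit means | Paired change in those remaining | Mixed model |
|---|---|---|---|---|
| 30% | -0.57 | -0.86 | -0.41 | -0.45 |
| 50% | -0.95 | -1.26 | -0.72 | -0.78 |

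The visit means overstate the fall by 0.29 and 0.31. Paired change understates it by 0.16 and 0.23, and the mixed model by 0.12 and 0.17. So pairing does not remove selection; it ensures that the same patients stand on both sides of the comparison. In these runs 70% and 51% of baseline scores were zero, which shows how readily a floor can arise.

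**4. What the all-patient mean shows.** If pain-free patients do not change, all-patient change = share with pain × change in those patients. Assume a 60% fall from 4.5, which is -2.7. A one-third share gives -2.7/3 = -0.9, and a one-fifth share gives -2.7/5 = -0.54. These are two different quantities, and both are worth reporting.

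**5. Precision by baseline pain.** With an assumed SD of change of 2, the standard error in patients with baseline pain is 2/√6 = 0.82 if 20% of 30 have pain, 2/√9 = 0.67 if 30% do, and 2/√15 = 0.52 if 50% do.

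**6. Baseline.** Footnote 3 to the Schedule of Events has CRT completed before SABR; Section 9.1.3 also allows SABR towards the end of the CRT course. Either way, the pre-SABR score in these patients follows some radiotherapy. The pre-CRT score in Section 7.14 does not.

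**The case against.** The strongest reply is that the plan already answers its objective. The objective is to describe change in ratings; no pain-relief or pain-response endpoint exists. A mean over all treated patients is a legitimate description, and it also captures new pain in patients who had none. A reader might infer that this mean is an error because it dilutes relief. The documents do not support that, because relief in patients with pain is not the stated quantity. A reader might also infer that the fallback loses the objective. It does not: visit summaries on the same scale still describe the course of pain. Leaving a linear model under a strong floor effect is itself defensible. All of this stands.

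It can also be said that simple descriptive statistics do not exclude change from baseline, since Section 11.2.5 opens by promising change over time. That is fair, and so the criticism is that paired change is not named, not that it is ruled out. Nor does the section make the pre-SABR score the baseline; a model with time as a factor can carry the pre-CRT score as its own time point. The gap is only that baseline is undefined.

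Finally, survival-only follow-up is triggered by disease events and treatment, not by pain, and no passage links pain at entry to leaving. This stands too, so the direction of any distortion is unknown. It does not remove the point that the set of patients changes and that the fallback does not require the plan's authors to show by how much.

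**Conclusion.** The point holds in a limited form. If the fallback is used, differences between visit summaries can mix true change with a changing set of patients, and the plan names neither a paired change nor the number contributing at each visit.

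A reader might infer from the first row of the table that the fallback will show a spurious one-third improvement. The documents do not support that. Under the stated assumptions the visit mean could equally be unaffected or rise by 0.6. In the simulation, with heavier loss among patients with pain, the distortion was about 0.3 points.

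Pain is one of six descriptive secondary objectives, with no test, power or decision rule attached, so no error rate or sample size is affected. This is a cheap improvement in reporting.

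**What to change.** Amend Section 11.2.5 as follows:

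1. Keep the all-patient mixed model as the main description.
2. Define baseline as the earliest pre-radiotherapy score: the pre-CRT score where CRT was given, otherwise the pre-SABR score.
3. In the fallback, report paired change from baseline at each visit (median or mean, and the proportions improved, unchanged and worse) with the number of patients contributing, instead of visit summaries alone. It would also help to state what counts as a strong floor effect.
4. Add a supplementary description by baseline pain: within-patient change in those scoring 1 or more, and the proportion developing pain, with exact 95% CI, in those scoring 0.

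An ordinal mixed model need not be required. With 30 patients, many zeros and about 17 time points (pre-SABR, 8 cycles and 8 three-monthly visits), it may not be estimable.

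The cost is SAP wording, since the scores are already scheduled. There are two downsides. The subgroups will be small, with wide intervals. In a single-arm trial, patients selected for having pain at baseline will tend to improve through regression to the mean, and the report should state that caveat beside the result. Paired change also describes only those still attending, which is why the number at each visit must accompany it.
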